7.5 Secondary Analyses

Lugano Classification (Appendix 13.4) (19) will be used to evaluate efficacy in terms of ORR, CR, PR, SD. Progression-free survival (PFS) will be determined from the enrollment date until the earliest date of disease progression, as measured by investigator assessment of objective radiographic disease assessments per Lugano Classification, or death due to any cause if earlier. Progression-free survival data will be analyzed using Kaplan-Meier method, treating subjects with no observed death or progression as censored at the last valid radiologic assessment visit. Median PFS and 90% CI will be estimated.

Overall survival (OS) will be determined from the enrollment date until death. Survival data will be analyzed using Kaplan-Meier method, treating subjects with no observed death as censored at their last date known to be alive. Median survival and 90% CI will be estimated. Overall survival data will continue to be collected until 75% of subjects have died, have withdrawn consent, or are lost to follow-up.

The DOR is defined as the difference of the end of response and the start of response for subjects who have achieved a response. The start of a response will be the first visit where the subject achieves PR or better based on the Lugano Classification. The end of response will be the first visit where PD is assessed based on the Lugano Classification. Duration of response will be assessed using Kaplan-Meier method for subjects who achieve a response. Median duration and 90% CI will be estimated. Subjects who are still responding at the time of database freeze or discontinuation will be censored at the last valid radiologic assessment visit.

7.6 Other Analyses

Exploratory end points include exploration of health-related quality of life during therapy (HRQOL) using The FACT-lym questionnaire. This has been validated in subjects with various forms of lymphoma. It contains 42 items (questions) covering HRQOL and common lymphoma

Version 11.0 Page 55 of 72

symptoms and treatment side-effects. The questionnaire begins with the Functional Assessment of Cancer Therapy - General (FACT-G), which contains 27 items covering four core HRQOL subscales: Physical Wellbeing (7 items), Social/Family Wellbeing (7), Emotional Wellbeing (6), and Functional Wellbeing (7). The FACT-Lym also includes an Additional Concerns subscale (15 items), addressing issues typically experienced by lymphoma subjects. Some of the issues covered include pain, itching, night sweats, trouble sleeping, fatigue and trouble concentrating. The FACT-Lym also asks subjects about their concerns about lumps and swelling, fevers, infections, weight, appetite, emotional stability and treatment. Other exploratory endpoints include resolution of B symptoms (fevers over 100.4, drenching night sweats, weight loss of over 10%) and pruritus. We will also record the time it took between enrollment to resolution of these symptoms and the duration of the disease-related symptoms.

7.7 Subject Population for Analysis – Phase II

In order to be included in the tolerability review, a subject must have received the cohort-specific dose of itacitinib and everolimus for at least 75% of the days during the 28-day DLT surveillance period or have experienced a DLT. Additional subjects may be enrolled to achieve a minimum cohort size of 3, should withdrawal or dose interruptions/reductions result in a subject being non-evaluable. In order to be included in the efficacy evaluation, a subject must have received at least 21 days of study-specified therapy. Subjects who receive at least one dose of the combined treatment (itacitinib and everolimus) will be assessed for adverse events, survival and exploratory analyses (FACT-lym, resolution of B symptoms or pruritus).

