Up to 2 years (24 cycles; each cycle is 28 days) of active therapy. Additional cycles of investigational treatment may be added if in the opinion of the investigator that the benefit risk ratio for the subject continues to be favorable. Subjects who discontinue study treatment will be followed for disease status, subsequent anticancer treatments, and survival for up to 2 years from completing end of treatment (EOT) visit. The study will end after the last subject completes 2 year follow-up or earlier once all subjects have discontinued study treatment, all subjects have died, have withdrawn consent, or are lost to follow-up.

Statistical Methodology

Sample size determination: Phase I portion of the study will utilize the standard 3 + 3 design with 6 to 15 patients enrolled. At least 6 patients will need to be treated at recommended phase 2 dose (RP2D) before proceeding to Phase II. A Simon optimal 2-stage design will be implemented to rule out the null CR rate of 5% against the alternative of 25% CR rate that might lead to larger, confirmatory studies. For 80% power and 5% alpha level, the first stage will enroll up to 9 evaluable subjects. If by week 16 there are no responders from the first 9 evaluable subjects with CR, the study will be stopped. Otherwise, additional subjects will be enrolled for a total of 8-17 evaluable treated at RP2D.

The study will be considered successful if 2 or more subjects achieve CR. Evaluable subject is defined as any subject who received at least 21 days of therapy and with at least one efficacy evaluation measured.

General data analysis plan: Descriptive statistics such as mean, standard deviation, median and range for continuous variable, and percentage for categorical variables will be computed. For the safety objective, all AEs will be listed and tabulated by organ system and in CTCAE preferred terms. Point estimate of the true AE rate and 90% exact confidence intervals will be computed. For the primary efficacy objective, a two-sided 90% confidence interval will be calculated for the CR rate as well as for the ORR. Duration of response, PFS, and OS will be summarized using Kaplan-Meier curve, and median survival time will be estimated with the associated 90% CI. FACT-Lym questionnaires will assess health related QOL.

Safety Evaluations

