3.1.3 Study Intervention Phase II

Subjects with cHL will receive the recommended Phase II dose (RP2D) of itacitinib in combination with everolimus as determined in Phase 1. Phase II will enroll 8 to 17 subjects depending on Cohort expansion in the Phase I portion. Since 6 of the Phase I subjects will be recruited, treated and followed in the same way as the Phase II subjects, they will be considered as accrued to the Phase II study as well. At least 14 subjects will be treated at RP2D level and evaluable for CR rate. Using a Simon 2-stage optimal design, if there are no responders with CR by the 16 week response assessment from the first 9 evaluable subjects at the RP2D, the null hypothesis will be considered as supported, and the study will be terminated. If there are no CRs in the first several patients (week 8 or 16 assessment), we will suspend the study enrollment and await final response assessment on all 9 patients (until week 16). The study will be considered successful if the total number of subjects with CR is \geq 2 in Phase II.

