3.3.2 Phase II

3.3.2.1 Primary Phase II Endpoints

• Efficacy will be assessed by CR rate, defined as the percentage of subjects achieving CR as their best response.

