4.5 Total Number of Subjects and Sites

The total planned number of evaluable subjects at UPenn will be 23 (including those in Phase I and II portions). To complete Phase I portion utilizing the 3 + 3 design, it is expected that 6 to 12 subjects will be enrolled. For phase II, 11 to 17 subjects will be enrolled. It is expected that total of 17-20 subjects will be treated at the RP2D dose since 3 to 6 patients from Phase I will be treated under the same regimen as Phase II patients. In order to be included in the tolerability review of Phase I, subjects must have received the cohort-specific dose of itacitinib and everolimus for at least 75% of the days during the first 28-day surveillance period or have experienced a DLT. Up to 5 additional subjects may be enrolled to achieve a minimum cohort size should withdrawal or dose interruptions/reductions result in subjects being non-evaluable during Phase I.

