7.3 Subject Population for Analysis – Phase I

In order to be included in the tolerability review, a subject must have received the cohort-specific dose of itacitinib and everolimus for at least 75% of the days during the 28-day DLT surveillance period or have experienced a DLT. Additional subjects may be enrolled to achieve a minimum cohort size of 3-6 (see Figure 1) should withdrawal or dose interruptions/reductions result in a subject being non-evaluable. Subjects who receive at least one dose of the combined treatment (itacitinib and everolimus) will be assessed for adverse events, response, survival and exploratory analyses (FACT-lym, resolution of B symptoms or pruritus).

Page 54 of 72

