7.4 Primary Analyses

The primary endpoint of Phase I is safety and tolerability by evaluating the frequency, duration, and severity of AEs as assessed by the investigators using CTCAE v5.0 criteria. The primary endpoint of Phase II is CR rate; a subject will be considered as a complete responder if his or her best overall response is CR on the Lugano Classification (Appendix 13.4) (Cheson et al 2014). The rate of responders will be estimated together with 90% confidence interval (CI). The study will be considered successful if the total number of complete responders is ≥ 2 in Phase II.

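### The Phase II CR rate drops early stoppers instead of counting them as non-CR, and the success rule counts CR over two different time windows

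*Combined protocol and SAP*

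**What the plan says.** **Who is counted.** Section 7.7 sets the Phase II efficacy population: "In order to be included in the efficacy evaluation, a subject must have received at least 21 days of study-specified therapy". The Study Summary (Statistical Methodology) adds a second condition: "Evaluable subject is defined as any subject who received at least 21 days of therapy and with at least one efficacy evaluation measured". Accrual is expressed in the same unit. Stage 1 is the first 9 evaluable subjects, after which "additional subjects will be enrolled for a total of 8-17 evaluable treated at RP2D".

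In Phase II, the set with at least one dose is used for adverse events, survival and exploratory analyses; response is not listed. The parallel Phase I sentence in section 7.3 does list it: "Subjects who receive at least one dose of the combined treatment (itacitinib and everolimus) will be assessed for adverse events, response, survival". Section 3.1.3 then pools Phase I subjects into the Phase II analysis: "Since 6 of the Phase I subjects will be recruited, treated and followed in the same way as the Phase II subjects", and they count as accrued to Phase II.

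**When a CR counts.** Section 3.3.2.1: "Efficacy will be assessed by CR rate, defined as the percentage of subjects achieving CR as their best response". Section 7.4: "a subject will be considered as a complete responder if his or her best overall response is CR on the Lugano Classification", with success at 2 or more such responders. Neither sets a time limit. Sections 7.2.1 and 8.7 state the same threshold of 2 but restrict it, in parentheses, to CRs at the week 8 or week 16 assessment. Section 6.7 continues scans every 16 weeks on treatment after week 16.

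**The concern.** A treated subject who stops before day 21 because of toxicity, progression or death is very unlikely to be a CR. Under 7.7 that subject leaves the denominator, and no passage brings the subject back as a non-CR. The CR rate and its 90% CI then describe those who tolerated the first three weeks, while the comparison is with a fixed 5% and there is no control arm in which the same selection would cancel. Because accrual runs to evaluable subjects, the place can also be refilled, and then the error rates of the decision rule change too.

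It is also unclear which population rule governs the six pooled Phase I subjects: the one-dose rule for response in 7.3 or the 21-day rule in 7.7.

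The window conflict needs no assumption. A first CR at the week 32 scan counts under 7.4 and does not count under 7.2.1 and 8.7. With 17 subjects and a threshold of 2, one such subject can decide the verdict, and the choice of rule could be made after the data are seen.

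**Working it through.** **Inputs from the documents.** Section 7.1: null CR rate 5%, alternative 25%, one-sided alpha 0.05, 80% power, 17 subjects at the RP2D, stop if 0 CR in the first 9. Sections 7.2.1, 7.4 and 8.7: success at 2 or more CRs.

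**Reproducing the design.** With p the CR rate, X1 the CRs in the first 9 and X2 those in the next 8:

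- P(success at 2 or more) = 1 − P(X1=0) − P(X1=1)·P(X2=0)
- At p = 0.05: 1 − 0.6302 − 0.2985 × 0.6634 = 0.1717.
- For 3 or more, also subtract P(X1=1)·P(X2=1) + P(X1=2)·P(X2=0) = 0.2985 × 0.2793 + 0.0629 × 0.6634 = 0.0834 + 0.0417. Result: 0.0466.
- At p = 0.25, power is 0.902 (2 or more) and 0.812 (3 or more).

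A search over two-stage designs gives 0/9 then 17 as the optimal design, with success at 3 or more. So 17 subjects and 80% power reproduce, but the printed cut-off of 2 does not hold alpha at 0.05. That is a separate matter; both cut-offs are shown so that it is not mixed with this one.

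**Denominator.** Assume a share d of treated subjects is excluded, all non-CR, and replaced. A true all-treated rate of 5% becomes 0.05/(1 − d) among evaluable subjects. The documents give no Phase II value for d. The spare places in section 4.5 cover dropouts that "result in subjects being non-evaluable during Phase I", so they do not supply one. Range used: 5–20%.

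| d | CR rate among evaluable | Type I error, 2 or more | Type I error, 3 or more |
|---|---|---|---|
| 0 | 5.0% | 17.2% | 4.7% |
| 5% | 5.3% | 18.6% | 5.3% |
| 10% | 5.6% | 20.2% | 6.0% |
| 20% | 6.3% | 24.0% | 8.0% |

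Exclusions unrelated to outcome would make these increases smaller. Without replacement the CR count, and so the verdict, does not change.

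**Reported rate, example.** 3 CRs in 20 treated: 3/20 = 15.0%, exact (Clopper–Pearson) 90% CI 4.2–34.4%. With 3 early failures removed: 3/17 = 17.6%, 90% CI 5.0–39.6%.

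**Window.** Assume a best-response CR rate of 25% and let q be the share of CRs reached by week 16 (assumed; not in the documents). The week-16 rule is the two-stage calculation with p = 0.25q. The best-response rule keeps the week-16 gate at 9 subjects but counts late CRs at the end. With the same gate, every week-16 success is also a best-response success, so the difference is the share of trials in which the two rules disagree.

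| q | Cut-off | Week-16 rule | Best-response rule | Disagree |
|---|---|---|---|---|
| 1.0 | 2 or more | 90.2% | 90.2% | 0% |
| 0.8 | 2 or more | 81.5% | 84.8% | 3.3% |
| 0.6 | 2 or more | 66.8% | 75.5% | 8.7% |
| 1.0 | 3 or more | 81.2% | 81.2% | 0% |
| 0.8 | 3 or more | 66.3% | 77.1% | 10.8% |
| 0.6 | 3 or more | 45.6% | 69.4% | 23.8% |

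**The case against.** **Replacement is one reading.** Sections 3.1.3 and 7.1 ask for at least 14 subjects treated at the RP2D and evaluable for CR rate, which could mean attrition from 17 treated to 14 evaluable with no topping up. The only explicit replacement sentence in 7.7 concerns the tolerability cohort. This does not settle the matter: 14 equals 6 Phase I plus 8 Phase II subjects and is itself a count of evaluable subjects. What stands is that the type I effect is conditional on replacement.

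**The 24% borrows from another defect.** Correct: the 17.2% starting point comes from the cut-off of 2. The denominator's own contribution is the increment, which is modest.

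**An evaluable set is an explicit, common choice, and all dosed subjects are followed for response (6.9.1).** Following subjects does not put them in the denominator. An evaluable set is defensible as a sensitivity analysis; as the only CR analysis, with early failures left out, it is not.

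**The pooled Phase I subjects fall under 7.7.** That is the natural reading of 3.1.3, but 7.3 gives a different response rule for the same people and no sentence says which prevails.

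**Few will be lost for want of a scan.** This is fair: Table 9 schedules imaging at end of treatment, so the Study Summary's second condition may add few exclusions to the 21-day rule.

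Nothing was found that reconciles the two CR windows.

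**Conclusion.** Both parts hold. The window conflict is the firmer: the primary success rule contradicts itself as written, whatever the assumptions. Its frequency depends on how many CRs come late. At a 25% CR rate the rules disagree in 3–9% of trials at 2 or more (11–24% at 3 or more) if 80–60% of CRs are reached by week 16.

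The denominator rule biases the reported CR rate upward if any treated subject stops early for toxicity, progression or death. Under 5–20% exclusion, all non-CR and replaced, it adds about 1.4 to 6.9 percentage points of type I error at 2 or more (18.6 − 17.2 to 24.0 − 17.2, before rounding) and 0.6 to 3.3 points at 3 or more. Without replacement it affects only the estimate and its interval. This should be corrected before the results are read; it does not undermine the design.

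**What to change.** 1. In 7.7 and the Study Summary, count as evaluable and not CR every subject treated at the RP2D, including the pooled Phase I subjects, who stops before day 21 or before any response assessment because of toxicity, progression or death.
2. Allow replacement only for reasons unrelated to outcome, for example loss of everolimus supply.
3. Keep the 21-day set as a sensitivity analysis.
4. Use one CR window for success in 3.3.2.1, 7.2.1, 7.4 and 8.7. Best response is the declared endpoint and the natural choice: delete the week 8/week 16 parenthesis from the success sentences in 7.2.1 and 8.7, and keep week 16 for the stage 1 gate. A fixed week-16 window would also work if 3.3.2.1 and 7.4 were changed to match.
5. State that the 5% and 25% refer to that same endpoint, among treated subjects.

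**Cost.** Wording only; 6.9.1 already plans response follow-up of everyone dosed. The reported CR rate may be slightly lower. With the week-16 gate and best-response success, power at a 25% CR rate is 85% if 80% of CRs are early and 75% if 60% are (2 or more), or 77% and 69% (3 or more), against 90% and 81% if all are early. If the 25% was meant among evaluable subjects only and 10–20% of treated subjects are early failures, the all-treated rate is 22.5–20%. Power, with all CRs early, is then 86–82% at 2 or more and 75–66% at 3 or more, which is why item 5 matters.

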8 SAFETY AND ADVERSE EVENTS

8.1 Definitions

Adverse Event

An adverse event (AE) is any untoward medical occurrence associated with the use of a drug in humans, whether or not considered drug related. Intercurrent illnesses or injuries should be regarded as adverse events.

A pre-existing condition should be recorded as an adverse event if the frequency, intensity or the character of the condition changes.

Abnormal Laboratory Values

A clinical laboratory abnormality should be documented as an adverse event if any of the following conditions is met:

- The laboratory abnormality is not otherwise refuted by a repeat test to confirm the abnormality.
- The abnormality suggests organ toxicity.
- The abnormality is of a degree that requires active management.

Page 56 of 72

Serious Adverse Event

Adverse events are classified as serious or non-serious. A serious adverse event is any AE that, in the view of either the investigator or the sponsor, is:

- fatal
- life-threatening
- requires or prolongs hospital stay
- results in persistent or significant disability or incapacity
- a congenital anomaly or birth defect
- an important medical event

Important medical events are those that may not be immediately life threatening, but are clearly of major clinical significance. They may jeopardize the subject, and may require intervention to prevent one of the other serious outcomes noted above. For example, drug overdose or abuse, a seizure that did not result in in-subject hospitalization, or intensive treatment of bronchospasm in an emergency department would typically be considered serious.

Dose Limiting Toxicity

See section 3.2 for a description of the Dose Limiting Toxicities (DLT).

8.2 Expected Adverse Events

Refer to the itacitinib Investigator's Brochure and the everolimus package insert for the expected adverse events.

8.3 Recording of Adverse Events

Safety will be assessed by monitoring and recording potential adverse effects using the Common Toxicity Criteria version 5 at each study visit. Participants will be monitored by medical histories, physical examinations, and other studies. If CTCAE grading does not exist for an adverse event, the severity of mild, moderate, severe, life-threatening, and death, corresponding to Grades 1-5, will be used whenever possible.

At each contact with the subject during the treatment phase of the study (before EOT), the investigator will seek information on adverse events by non-directive questioning and, as appropriate, by examination. Adverse events may also be detected when they are volunteered by the subject during the screening process or between visits, or through physical examination, laboratory test, or other assessments. Information on all adverse events will be recorded in the source documentation. To the extent possible, adverse events will be recorded as a diagnosis and symptoms used to make the diagnosis recorded within the diagnosis event.

As much as possible, each adverse event or follow-up information will be evaluated to determine:

- 1. Severity grade (CTCAE Grade 1-5)
- 2. Duration (start and end dates)

Page 57 of 72

- 3. Relationship to the study treatment or process [Reasonable possibility that AE is related: No (unrelated/ not suspected) or Yes (a suspected adverse reaction)]. If yes (suspected) is the event possibly, probably or definitely related to the investigational treatment?
- 4. Expectedness to study treatment or process [Unexpected if the event severity and/or frequency is not described in the investigator brochure (if applicable) or protocol].
- 5. Action taken with respect to study or investigational treatment or process (none, dose adjusted, temporarily interrupted, permanently discontinued, unknown, not applicable)
- 6. Whether medication or therapy taken (no concomitant medication/non-drug therapy, concomitant medication/non-drug therapy)
- 7. Whether the event is serious

Once an adverse event is detected, it should be followed until its resolution, the end of study visit, or until it is judged to be permanent, and assessment should be made at each visit (or more frequently, if necessary) of any changes in severity, the suspected relationship to the study treatment, the interventions required to treat it, and the outcome. Related AEs should be followed until resolution, lost to follow up, or judged to be permanent.

8.4 Reporting of Adverse Events, Adverse Device Effects and Unanticipated Problems

Reporting period

Adverse events will be reported from the time of informed consent until EOT visit. Once a subject enters into the safety follow up period as described in section 6.4.8, subjects will only be followed for unresolved adverse events.

Investigator reporting: notifying the study sponsor

Every SAE, regardless of suspected causality (e.g., relationship to study drug(s) or study procedure or disease progression) must be reported to the sponsor within 24 hours of learning of its occurrence.

Recurrent episodes, complications, or progression of the initial SAE must be reported as the follow-up to the original episode within 24 hours of the investigator receiving the follow-up information. An SAE considered completely unrelated to a previously reported one should be reported separately as a new event.

Send the notification (MedWatch or CIOMS form) to the Sponsor.

New information regarding the SAE will be reported as it becomes available and in the same manner as the initial SAE (i.e. MedWatch or CIOMS). The investigator must follow the event to resolution or until the event is deemed and documented irreversible, whichever is longer, up to 6 months from the last treatment.

Version 11.0 Page 58 of 72

Investigator Reporting: Local Reporting Requirements

The investigator will report AEs and SAEs to his/her IRB/EC of record and other local regulatory groups per the local requirements.

